#### **12.5 Reporting of Serious Adverse Events and Suspected Unexpected Serious Adverse Reactions**

In accordance with ICH guidelines for GCP, a copy of the written report of any SAEs should promptly be sent to the study Sponsor. The Investigator must notify Sponsor and Sponsor’s designated study safety officer within 24 hours of becoming aware of the occurrence of an SAE.

Information regarding SAEs will be transmitted to the Sponsor and Sponsor’s designated study safety officer using an SAE form as described in the study SAE Report Form Completion Guidelines. The SAE form must be completed and signed by a member of the investigational staff and transmitted to the Sponsor and Sponsor’s designated study safety officer within 24 hours ([Table 12-C](#)). New or updated information on the SAE will be recorded on a new SAE form and sent to the Sponsor and Sponsor’s designated study safety officer within 24 hours of the information being available. The initial and follow-up reports of an SAE should be made by e-mail.

## 12.6 Follow-up of Adverse Events and Serious Adverse Events

After the initial AE/SAE report, the Investigator is required to proactively follow each participant and provide further information to the Sponsor on the participant's condition.

All AEs and SAEs documented at a previous visit/contact that are designated as ongoing, will be reviewed at subsequent visits/contacts. If these have resolved, this should be documented. AEs/SAEs that have not resolved by the end of the study, or that have not resolved upon discontinuation of the participant's participation in the study, must be followed until any of the following occurs:

- The event resolves.
- The event stabilises.
- The event returns to Baseline, if a Baseline value is available.
- The event can be attributed to agents other than the study drug or to factors unrelated to study conduct.
- It becomes unlikely that any additional information can be obtained (participant or health care practitioner refusal to provide additional information, lost to follow-up after demonstration of due diligence with follow-up efforts).

The Investigator will ensure that AE/SAE follow-up includes any supplemental investigations as may be indicated to elucidate the nature and/or causality of the event. This may include additional laboratory tests or investigations, histopathological examinations, or consultation with other health care professionals.

The Sponsor may request that the Investigator perform or arrange for the conduct of supplemental measurements and/or evaluations to elucidate as fully as possible the nature and/or causality of the AE/SAE. If a participant dies during participation in the study or during a recognised follow-up period, where possible, the Sponsor will be provided with a copy of any post-mortem findings, including histopathology.

## **12.7 Exposure *In Utero* Management and Reporting**

Dosing of the study drug must be discontinued immediately in instances of pregnancies or suspected pregnancies (including a positive pregnancy test regardless of age) in a participant that is on investigational product (including the female partner of a male participant).

The Investigator will notify the Sponsor and designated study safety officer of any pregnancy he/she becomes aware of in female participants or the partners of male participants using an exposure-in-utero form. The pregnant participant (or the male participant's pregnant partner) should be advised to call her healthcare provider.

The Investigator shall obtain informed consent from the pregnant participant (or male participant's pregnant partner) in order to the Investigator (or delegate) to conduct follow-up throughout the gestational period and on the infant following delivery. The Investigator shall follow-up newborn infants that have been exposed to investigational product *in utero* for a minimum of 12 months. Upon discovery of any congenital anomalies (or neonatal deaths) the Investigator shall submit a follow-up report to the Sponsor and Sponsor's designated study safety officer using an SAE form including information regarding the status of the newborn. A miscarriage or any abortion shall also be reported by the Investigator to the Sponsor and Sponsor's designated study safety officer using an SAE form (as per the study SAE Report Form Completion Guidelines).

## 13 STATISTICS AND DATA ANALYSIS

Detailed methodology for the summation and statistical analysis of the data collected will be documented in a separate Statistical Analysis Plan (SAP) that will be finalised before database lock. Any changes to the methods described in the final SAP will be described and justified as needed in the clinical study report (CSR).

This section describes the general framework to be used for the analysis and presentation of data in this study. The information described in this section may be revised during the study to accommodate protocol amendments and to make changes to adapt to unexpected issues in study execution and data that could affect planned analyses.

Generally, summaries will be presented separately for Parts A and B, with summaries presented by treatment group and overall for Part B.

For descriptive statistics, continuous data will be summarised by treatment arm and time point using the number of observations, arithmetic mean, standard deviation (SD), median, minimum and maximum. Discrete data will be summarised using counts and percentages.

All available data will be included in data listings. Data tabulations will be performed for specific analysis populations.

### 13.1 Sample Size Considerations

The total study sample size was selected to have a high probability of detecting one or more serious adverse events (SAE) if the SAE event rate is 10% or more. If the probability of an SAE is 10%, the probability of observing at least one event in N=35 subjects is over 97%. Looking at Part B only, if the probability of an SAE is 10%, the probability of observing at least one event in N=30 subjects is over 95%.

### 13.2 Analysis Populations

#### Full Analysis Set

The Full Analysis Set will include all enrolled participants.

#### Safety Analysis Set

All participants who receive any study drug will be included in the Safety Analysis Set and will be analysed as per the actual treatment received, if this differs from that to which the participant was randomised.

#### Pharmacokinetic Analysis Set

The PK Analysis Set will include all participants in the Safety Analysis Set who have at least one study drug concentration determined.

#### Immunogenicity Analysis Set

The Immunogenicity Analysis Set will include all participants in the Safety Analysis Set who have sufficient data to derive at least one Immunogenicity parameter.

### 13.3 Disposition

The number of participants enrolled in the study, screen failed participants (if available), participants who completed the study, patients who prematurely withdrew from the study

(including reasons for withdrawal) and the number of patients in each analysis set will be summarized.

### **13.4 Demographic and Baseline Data**

Demographic and baseline data will be presented using the safety analysis set.

Demographic data (including gender, age, race, ethnicity, height, weight, and BMI) will be summarised using descriptive statistics.

Medical history will be coded using the latest version of the Medical Dictionary for Regulatory Activities (MedDRA). The number of participants reported with conditions/procedures and the number of conditions/procedures reported will be summarised, grouped according to system organ class (SOC) and preferred term, using descriptive statistics.

Assessments performed for eligibility only will be listed.

### **13.5 Prior and Concomitant Medication Data**

Prior and concomitant medication data will be presented using the safety analysis set.

Prior and concomitant medications will be coded using the latest version of the World Health Organisation Drug Dictionary (WHO DD). The number and percentage of participants taking prior medication, and concomitant medication will be summarised using frequency tables according to WHO Drug Anatomical Therapeutic Chemical (ATC) Classification Level 1 Code Description and the WHO DD Preferred Name. If a participant has more than one prior or concomitant medication coded to the same preferred name, the participant will be counted only once in the summaries.

### **13.6 Treatment Compliance and Exposure Data**

Treatment compliance and exposure data will be presented using the safety analysis set and full analysis set.

Treatment exposure and compliance will be summarised using descriptive statistics and presented by treatment group and overall.

### **13.7 Safety and Tolerability Data**

All safety analysis will be performed using the safety analysis set.

#### *13.7.1 Adverse Event Data*

All AEs will be coded using the latest version of MedDRA by SOC and preferred term, classified from verbatim terms. The number of treatment-emergent AEs (TEAEs) as well as the number and percentage of participants with at least one TEAE, will be summarised by SOC and preferred term. Summaries of TEAEs by severity and relationship will also be presented. Summaries will also be presented for SAEs, TEAEs leading to death or study withdrawal. The duration of all AEs will be determined and included in the listings.

Solicited and unsolicited TEAEs will also be summarised separately. Further details will be provided in the SAP.

### *13.7.2 Vital Signs*

Observed values and changes from baseline for vital signs (systolic and diastolic blood pressure, pulse rate, oral temperature, and respiratory rate) will be summarised at each scheduled timepoint using descriptive statistics.

### *13.7.3 Nasal Examinations*

Nasal examination findings will be listed. Any post-dose clinically significant findings will be reported as AEs.

### *13.7.4 Physical Examination Data*

Physical examination data will be listed only. Any post-dose clinically significant findings will be reported as AEs.

### *13.7.5 Clinical Laboratory Safety Data*

Clinical laboratory safety data will be summarised by laboratory parameter. Observed values and changes from baseline for continuous clinical laboratory parameters will be summarised at each scheduled timepoint using descriptive statistics. Categorical clinical laboratory data will be summarised at each scheduled timepoint using participant counts and percentages. The clinical assessment of laboratory data will be summarised at each scheduled timepoint using participant counts and percentages. Individual participant profiles will be presented for any laboratory parameters with at least one post-dose value outside the laboratory's reference ranges that is deemed clinically significant.

### *13.7.6 Electrocardiogram*

For ECG data, replicate values will be averaged to determine the value of the ECG parameter at each timepoint.

The following ECG parameters will be analysed: PR interval, QRS duration, QTcB, QTcF and ventricular heart rate. Observed values and changes from baseline for ECG parameters will be summarised at each scheduled timepoint using descriptive statistics.

For QTcF, the number of participants with values greater than 450 (and 480, 500) msec or an increase from baseline of at least 30 (and 60) msec will also be tabulated, in accordance with ICH E14 (Note for guidance on the clinical evaluation of QT/QTc interval prolongation and proarrhythmic potential for non-antiarrhythmic drugs, CHMP/ICH/2/04).

### *13.7.7 Nasal Symptoms Sino-Nasal Outcome Test*

Scores will be totalled for all 22 symptoms. Changes from baseline in individual total SNOT-22 scores will be calculated as the post-baseline value minus the baseline value. Thus, a negative change will reflect an improvement in the corresponding score. Observed values and changes from baseline will be summarised at each scheduled timepoint by treatment using descriptive statistics and tabulated for each cohort (dose level) and overall.

Individual symptoms will be listed, with the 5 most important issues flagged. The total SNOT score will also be included in the listing.

### **13.8 Pharmacokinetic Data**

All PK analysis will be conducted using PK Analysis Set. Participants with dosing deviations that could potentially affect the PK profile may be excluded from the PK parameter evaluation, at the discretion of the study pharmacokineticist.

Individual participant LMN-301 plasma and nasal mucosal lining fluid concentrations will be listed and summarised using descriptive statistics (n, mean, standard deviation, coefficient of variation [%CV], minimum, maximum, median, geometric mean and geometric coefficient of variation). Individual and mean LMN-301 plasma concentrations over time will be presented graphically with concentration displayed on a linear and a logarithmic scale for each dose group using nominal time points.

Summaries (frequency, means, etc.) will be generated and presented in tabular and/or graphical form.

Due to the sparseness of the PK sampling scheme, no PK parameters will be determined. Serum and nasal drug concentrations be determined at the timepoints presented in [Table 21-C](#) and [Table 21-D](#), and will be presented in tabular or graphical form, as appropriate.

If the overall test for group differences is significant, pairwise comparisons between groups will be generated adjusting for multiple comparisons. Additional details will be presented in the SAP.

### **13.9 Immunogenicity Data**

Immunogenicity data will be analysed using the Immunogenicity Analysis Set.

For Part A, serum anti-LMN-301 antibody (possibly binary yes/no, titer, neutralizing) on Day 1 (predose), Day 1 (postdose) and Day 8 will be reported for each subject and presented in tabular or graphical form.

For Part B, serum anti-LMN-301 antibody (possibly binary yes/no, titer, neutralizing) on Day 1 (predose), Day 1 (post dose), Day 3 or 4 (predose), Day 7 (predose) and Day 14 will be reported for each subject and presented in tabular and/or graphical form.

Summaries (frequency, means, etc.) will be generated and presented in tabular and/or graphical form.

If the overall test for group differences is significant, pairwise comparisons between groups will be generated adjusting for multiple comparisons. Additional details will be presented in the SAP.

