### 6.3 Part B (Multiple Dose)

Up to 30 participants will be sequentially assigned to one of three dosing groups (10 participants per group) starting with Group 1. Participants will be administered LMN-301 intranasally to each nostril at a fixed dose of 50 mg (25 mg in each nostril) every third day for 12 days (Group 1), every other day for 12 days (Group 2) or every day for 12 days (Group 3). All study participants will be observed in the clinic for 4 hours after the first dose.

Participants will be monitored for the occurrence of any adverse events (AEs) and serious adverse events (SAEs). Vital signs, physical exams and safety/laboratory testing will be performed on Days 1, 3 or 4, 7 and 14. Participants will use a diary (paper or electronic) to record any symptoms from the first dose through 28 days after the first dose.

Serum will be collected on Days 1 (baseline before dosing and 2 hours after dosing), 3 or 4, 7 and 14 for analysis to detect systemic absorption of virus-binding proteins and anti-drug antibodies (ADA).

Nasal mucosal lining fluid (MLF) samples will be collected using Synthetic Absorptive Matrix (SAM) strips (Nasosorption™ FX-I, Hunt Developments (UK) Ltd, United Kingdom) from all participants on Day 1 (baseline before dosing and 2 hours after dosing), and on Days

3 or 4, 7 and 14. Nasal MLF samples will be sent to Lumen Bioscience (Seattle, WA, USA) for analysis.

The schedule of assessments (SoA) for part B is presented in [Table 21-B](#) with a description of the study schedule and procedures provided in [Sections 10 and 11](#).

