## 6.7 Treatment Allocation

All study participants who sign an informed consent form at screening will receive a unique sequential number (i.e., a screening number). Participants will be allocated to the next available treatment group in the order they are screened. As this is an open-label study, no randomisation or blinding will occur.

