4.4 Multiple Comparisons and Multiplicity

A Bonferroni correction will be explored for Immunogenicity model analysis (Section 15). Both adjusted and unadjusted p-values will be presented.

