15 IMMUNOGENICITY

Immunogenicity analysis will be conducted outside of Avance and will be detailed in a separate Immunogenicity Analysis Plan.

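### Part B drug-level and antibody data are to be tested for significance between unrandomised, sequentially filled groups, so a group difference cannot be separated from enrolment order, and the planned adjustment does not cover the choice of readout and time point

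*Protocol*

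**What the plan says.** **The testing rule.** Protocol 13.9 says of the antibody data: "If the overall test for group differences is significant, pairwise comparisons between groups will be generated adjusting for multiple comparisons". Protocol 13.8 repeats the sentence for serum and nasal drug levels; nasal levels are the secondary endpoint. Neither section gives the test, the alpha, the readout, the time point, or whether Part A is included. Section 13.9 lists five Part B samples (one pre-dose, four post-dose) and three possible forms of antibody result without choosing among them.

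**Where the detail should be.** Protocol 13.9 adds: "Additional details will be presented in the SAP". SAP 4.4 offers: "A Bonferroni correction will be explored for Immunogenicity model analysis (Section 15)", followed by "Both adjusted and unadjusted p-values will be presented". SAP 15 holds no model; it says: "Immunogenicity analysis will be conducted outside of Avance and will be detailed in a separate Immunogenicity Analysis Plan". SAP 14 defers PK in the same way, and SAP 4.4 does not mention PK. SAP 16 records one departure from the protocol, concerning Protocol 13.6, so the tests in 13.8 and 13.9 still stand.

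**Allocation.** Protocol 6.3: "Up to 30 participants will be sequentially assigned to one of three dosing groups (10 participants per group) starting with Group 1". Protocol 6.7: "Participants will be allocated to the next available treatment group in the order they are screened" and "As this is an open-label study, no randomisation or blinding will occur".

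**The concern.** In a randomised comparison, allocation itself justifies reading a small p-value as evidence about treatment. Here regimen follows order of entry. Anything that changes over recruitment, such as the mix of volunteers, background exposure to the virus, sampling technique or assay calibration, can move the groups apart when dosing frequency has no effect. A multiplicity correction limits chance findings; it cannot remove a bias of this kind.

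The second gap is selection. With several readouts and several visits, an overall test could be run on each. Adjusting the three pairs inside one overall test does nothing about how many overall tests are run or which is reported.

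The risk is that an artefact of recruitment, batch or selection is reported as an effect of dosing frequency on nasal persistence or antibody formation, and carried into the choice of regimen for later work.

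**Working it through.** **1. The plan's own figure.** The only sample-size basis (Protocol 13.1, SAP 3) is the chance of seeing at least one SAE at a true rate of 10%, which is 1 − 0.9^N:
- N = 35: 1 − 0.9^35 = 97.5%, stated as over 97%.
- N = 30: 1 − 0.9^30 = 95.8%, stated as over 95%.

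Both reproduce. Nothing sizes the study for comparing groups.

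**2. Number of overall tests the wording could allow.** Three antibody forms × 4 post-dose times = 12. Two matrices (serum, nasal fluid) × 4 post-dose times = 8. Total 20. The documents do not commit to this grid; it is what they leave open.

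**3. Chance of at least one false positive** (alpha 0.05 assumed, because none is stated; no true differences). If the tests are independent, this is 1 − 0.95^k. For correlated tests it was simulated with three groups of 10, one-way ANOVA and equal correlation.

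| Overall tests | Independent | Correlation 0.5 | Correlation 0.8 |
|---|---|---|---|
| 12 | 46% | about 33% | about 20% |
| 20 | 64% | about 43% | about 24% |

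One pre-specified overall test carries 5%.

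**4. Effect of drift with no regimen effect.** Assumptions: log10-scale readout, SD 0.5, 10 per group, a constant shift from each group to the next, Kruskal-Wallis test at 0.05. The shift sizes are assumed; the documents give none.

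| Shift per group (log10) | Group 1 to Group 3, in SD | Test rejects |
|---|---|---|
| 0 | 0 | about 4% to 5% |
| 0.05 | 0.2 | about 5% |
| 0.10 | 0.4 | about 10% |
| 0.15 | 0.6 | about 17% |
| 0.25 | 1.0 | 42% to 44% |

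The second column is 2 × shift / 0.5. Small drift does little; drift approaching one SD across the three groups matters.

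**5. What 10 per group can show.** Bonferroni over three pairs gives 0.05/3 = 0.0167. By Fisher's exact test, 5/10 v 0/10 gives p = 0.033, which fails that level; 6/10 v 0/10 gives p = 0.011, which passes. For a continuous readout, a pairwise t-test at 0.0167 needs a difference of about 1.57 SD for 80% power.

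**6. Sampling relative to dosing.** From the dosing days in Protocol 8.5, the pre-dose Day 7 sample falls 3, 2 and 1 days after the previous dose in Groups 1, 2 and 3 (7 − 4, 7 − 5, 7 − 6). Day 14 falls 4, 3 and 2 days after the last dose (14 − 10, 14 − 11, 14 − 12). The early sample is on Day 4 in Group 1 and Day 3 in the others. Even at a shared visit, then, a difference in nasal level partly reflects time since dosing.

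**The case against.** **Separate plans exist.** The PK and Immunogenicity Analysis Plans may name the test, readout and time point, and the Laboratory Manual may set the assay layout. This stands: a reader might infer that nothing is specified anywhere, but the documents support only that the protocol and SAP do not specify it. The protocol promised the detail in the SAP, and the SAP 4.4 cross-reference fails whatever the other plans say.

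**Error is partly controlled.** Pairwise tests are gated on an overall test and adjusted. This stands within one readout and time point, so it would be wrong to infer that there is no error control at all. It does not reach across readouts and time points, and unadjusted p-values are to be shown as well.

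**The 46% to 64% is not the plan's error rate.** This stands. No document plans 12 or 20 tests; the SAP speaks of a model, which could cover all visits at once. Titre and neutralising tests follow only if antibodies are confirmed (Protocol 11.18), and the synopsis and SAP 2.2.3 make the IgG test depend on finding drug in serum. Repeat samples from 30 people are correlated, and exact tests on a rare yes/no result reject less than 5% of the time.

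**Batch bias is not shown.** This stands. A reader might infer that the groups were assayed separately. Serum is frozen at −80°C until shipped, so a single mixed run is possible; the documents give no rule either way. The recruitment period is not stated, so the groups may also be close in time. Day 1 pre-dose samples would help to reveal drift.

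**Limited reach.** Only secondary and exploratory endpoints are involved, and no stated decision rests on these p-values. This limits the severity but does not make the comparison interpretable.

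**Conclusion.** The point holds in a limited form. The protocol commits to significance tests across unrandomised groups assigned in sequence, and no adjustment in the protocol or SAP can separate regimen from enrolment order. Confounding with assay batch is possible, not documented. The multiplicity provision is confined to pairs within one overall test, is only to be explored in the SAP, and leaves out PK.

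The size depends on assumptions. If one overall test is pre-specified and there is no drift, the false-positive risk is the assumed 5%. If 12 to 20 tests are run, it lies between about 20% and 64%, according to correlation. Under assumed drift of 0.05 to 0.25 log10 per group, one test rejects about 5% to 44% of the time with no regimen effect. None of these is an estimate of what will happen in this trial. A reader might infer that the safety conclusions are compromised; they are not, because the primary analysis is descriptive. This is a cheap improvement that should be made, not a fatal flaw.

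**What to change.** 1. In Protocol 13.8 and 13.9, replace the overall and pairwise tests with descriptive reporting by Part B group. Give the number with drug detected and the number with treatment-emergent antibodies (negative to positive, or a titre rise, relative to the Day 1 pre-dose sample), each with an exact 95% confidence interval. For 0/10 the upper limit is 1 − 0.025^(1/10) = 31%, which states openly what 10 people can show.
2. Assay stored samples with groups mixed across plates and each participant's samples on one plate. If assays have already been run, report the run layout by group.
3. If a between-group test is kept, pre-specify one readout at one time point and label it exploratory and non-randomised.
4. Align SAP 4.4, 14 and 15 and the two separate plans with that choice, remove the reference to an absent model, and record the change in SAP 16.

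The cost is wording in the protocol, SAP and two analysis plans, plus a plate layout. The downside is no confirmatory p-values between groups and some delay while samples are batched.
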